4.0 Treatment Methods

4.1 Radiation Treatment

Prior to treatment, all patients will provide informed written consent for radiation therapy as per existing institutional policy. All patients will undergo a computed tomography (CT) simulation for treatment planning. Radiation therapy will be delivered with an intensity modulated radiation therapy (IMRT) technique and/or image-guided radiation therapy (IGRT). The prescribed course of radiotherapy will not be altered based on this study. Radiotherapy will be delivered 5 days per week, Monday – Friday with one radiation treatment given per day. The planned cumulative dose of radiation will be determined by the treating physician and will range from 5000 – 7000 cGy in 180 - 200 cGy daily fractions over the course of 5-7 weeks. This treatment is not part of the research protocol.

4.1.1 Definition of Target Volumes:

Target volumes will be outlined per institutional practice and not modified based on this protocol. Target volumes are defined as the following:

Gross Tumor Volume (GTV) represents the region judged to contain gross primary tumor or involved node(s) based on clinical and endoscopic examinations, CT scan, and, when applicable, other imaging techniques.

Clinical Target Volume (CTV) is defined as the GTV plus areas considered at risk for containing microscopic disease delineated by the treating physician. The CTV margins can be narrower when GTV is in the proximity of the spinal cord or critical normal tissues.

Planning Target Volume (PTV) represents an additional margin around the CTV to compensate for the variability of treatment set up and internal organ motion.

4.1.2 Definition of Organs at Risk:

CT-based planning will be used to identify the target volumes and organs at risk (OARs). OARs will be contoured according to the DAHANCA, EORTC, GORTEC, HKNPCSG, NCIC CTG, NCRI, NRG Oncology, and TROG consensus guidelines [24] which are included in table 2 which is provided in appendix 11.4. The dose parameters given to OARs will be recorded (table 3). Dose limits to OARs will be determined by institutional practice and specific dose-constraints will not be required on this protocol. The following radiation doses will be recorded.

Table 3. Dose parameters to OARs to be recorded

Brainstem	Maximum Dose _____
Spinal Cord	Maximum Dose _____
Right Parotid	Mean Dose _____
	V30 _{Gy} _____
Left Parotid	Mean Dose _____
	V30 _{Gy} _____
Parotids (bilateral)	D20 _{cc} _____
Submandibular Gland	Mean Dose _____
Extended Oral Cavity	Maximum Dose _____
	Mean Dose _____
Lips	Maximum Dose _____
	Mean Dose _____
Buccal Mucosa	Maximum Dose _____
	Mean Dose _____
Mandible	Maximum Dose _____
Pharyngeal Constrictors	Mean Dose _____

4.2 Chemotherapy

Prior to treatment, all patients will provide informed written consent for chemotherapy as per existing institutional policy. The prescribed course of chemotherapy will be determined by the managing medical oncologist per institutional practices and will not be altered based on this study. The frequency and dose of chemotherapy will be recorded for each patient on the trial. This treatment is not part of the research protocol.

4.3 Low-LevelLaserTherapy

Treatment will be administered on an outpatient basis. While there are no expected toxicities, potential adverse events will be monitored per Section 7 (Adverse Events and Safety Monitoring). No investigational agents or therapies for the prevention of oral mucositis other than those described in this protocol may be administered.

LLLT will be delivered with the THOR® Laser system (THOR Photomedicine Ltd, Chesham, UK). LLLT will begin on the first or second day of radiotherapy and be delivered three times per week (e.g. Monday, Wednesday, and Friday) until the completion of radiotherapy. A trained radiation oncology nurse or physician will deliver treatment. LLLT may be delivered either immediately prior to or after the patient's daily fraction of radiotherapy. If it is determined that a break in radiotherapy is required for clinical reasons, LLLT will also be held. Patients will be treated extra-orally with a THOR® LED cluster for one minute along the cheek to treat the buccal mucosa on each side and intraorally for one minute to the tongue and soft palate. During each LLLT treatment session a thorough oral exam will be performed to identify any areas of mucositis. If the patient should develop intraoral lesions they will be targeted directly with the intraoral probe for one minute to each site of mucositis.

The laser settings to be used are as follows: frequency 2.5 Hz; wavelength 660 nm; and power 75 mW. The dose per anatomic site treated will be 4.5 J/cm². No dose modifications for the LLLT will be made.

The extra-oral probe will be cleaned before and after each use. Prior to each use, the intraoral probe will be covered with a protective dental sleeve. Patients and laser operator will wear THOR® laser safety glasses for the duration of laser therapy.

Treatment dates and sites will be recorded for each patient on the LLLT Treatment Record Form given in the appendix (appendix 11.3). Compliance with therapy will be documented. Subjects who miss >20% of planned LLLT treatments will be considered non-compliant with the protocol. For each treatment session, the dose will be set (timer on control unit) and the patient will be positioned comfortably a chair. The LLLT device will be for a minimum of 3 exposures:

1. Right cheek
2. Left cheek
3. Tongue/Soft palate

The treatment per site will take 60 seconds, for a minimum treatment time of three minutes. If any areas of mucositis are evident on examination at the time of LLLT treatment, each area will be targeted with an intraoral probe for an additional 60 seconds.

There will be no pre- or post-treatment measures/precautions.

4.4 Other treatments

Subjects that develop symptomatic mucositis will be managed as necessary according to standard standard of care hospital protocol for oral mucositis in addition to LLLT. This may include topical creams, pain medications, anesthetic mouth rinses, mouth coatings, and nutritional support with supplementation either by mouth or feeding tube, without the use of specific investigational, restricted agents. No standard treatment will be denied to a patient on this protocol.

5.0 Follow-up and Assessments

5.1 Followup Schedule

A general history & physical by a radiation oncologist and/or medical oncologist must be done within 8 weeks prior to registration. Patients will be evaluated for protocol eligibility at the time of initial consultation. At the time of initial evaluation, baseline assessments will be performed. During the course of treatment, each patient will be seen by the supervising physician in clinic for an on-treatment evaluation at least once per week (or at an interval of once per five radiation treatments). Follow-up appointments will be scheduled for two weeks and three months after the completion of therapy.

Table 4. Study Calendar Overview

Screening	Baseline	Treatment Period		Follow-up Period
		Assessments	LLLT Dosing	
Day -1 to Day -28	Study Day 0	Weekly Last day of treatment	3x/week concomitant with chemoradiation	Two weeks Three months

5.2 Follow-up Assessments

During each assessment, the following toxicities will be assessed: pain, OM, dysphagia, xerostomia, dysgeusia, dermatitis, trismus, and QOL.

Mouth pain and throat pain severity will be assessed weekly using a standard 0-10 scale. A record of the amount of analgesic medications required will be required at each visit.

A diet assessment will be performed at weekly on-treatment assessments as follows:

DietAssessment		

Diet1: What has the subject been able to eat within the past 24 hours (mark only one)
 
 Solids  Liquids  Nothing by Mouth
 
If Solids is marked above, proceed to next section. If Liquids or Nothing by Mouth is marked about continue to "Diet 2".
	
Diet2: If the subject has been unable to eat Solid food, mark all the reason(s) why (mark all that apply)
 
 Nausea/Vomiting  Loss of appetite  Throat discomfort  Difficulty Swallowing  Other _____
 
If Oraldiscomfort is marked above, proceed to the next section. If Oraldiscomfort is NOT marked above, proceed to "Diet 3".
	
Diet3: Based solely on how the mouth feels, what does the subject feel (s)he could try to eat if (s)he did not have to swallow (mark only one)
 
 Solids  Liquids  Nothing by Mouth

OM will be assessed using the NCI CTCAE version 4.0 [25] as follows:

Adverse Event	Grade				
	1	2	3	4	5
Oral Mucositis	Asymptomatic or mild symptoms; intervention not indicated	Moderate pain; not interfering with oral intake; modified diet indicated	Severe pain; interfering with oral intake	Life-threatening consequences; urgent intervention indicated	Death

OM will also be assessed using the World Health Organization (WHO) grading scale [26]:

WHO Oral Mucositis Grade	
Grade 0 (None)	None
Grade 1 (Mild)	Oral soreness/erythema
Grade 2 (Moderate)	Oral soreness/erythema, ulcers, can tolerate solid foods
Grade 3 (Severe)	Oral soreness/erythema, ulcers, liquid diet only
Grade 4 (Life-threatening)	Oral alimentation is not possible

Patient-reported OM outcomes will be assessed using the Oral Mucositis Daily Questionnaire (OMDQ) [27]

OralMucositisDailyQuestionnaire

2. During the PAST 24 HOURS how much MOUTH AND THROAT SORENESS DID YOU HAVE? (Circle one number)

0 No soreness	1 A little soreness	2 Moderate soreness	3 Quite a lot of soreness	4 Extreme soreness
------------------	------------------------	------------------------	------------------------------	-----------------------

3. During the PAST 24 HOURS how much did MOUTH AND THROAT SORENESS limit you in each of the following activities:

a. Swallowing	Not limited 0	Limited a little 1	Limited some 2	Limited a lot 3	Unable to do 4
---------------	------------------	-----------------------	-------------------	--------------------	-------------------

b. Drinking	0	1	2	3	4
c. Eating	0	1	2	3	4
d. Talking	0	1	2	3	4
e. Sleeping	0	1	2	3	4

4. On a scale of 0 to 10, how would you rate your OVERALL MOUTH AND THROAT SORENESS during the PAST 24 HOURS? (Please circle the most appropriate number)

*Questions 2 through 4 of OMDQ adapted from Elting et al, 2008 [27]

Dysphagia will be assessed using the NCI CTCAE version 4.0 [25] as follows:

Adverse Event	Grade				
	1	2	3	4	5
Dysphagia	Symptomatic, able to eat regular diet	Symptomatic and altered eating/swallowing	Severely altered eating/swallowing; tube feeding or TPN or hospitalization indicated	Life-threatening consequences; urgent intervention indicated	Death

Xerostomia will be assessed using the NCI CTCAE version 4.0 [25] as follows:

Adverse Event	Grade				
	1	2	3	4	5
Dry Mouth	Symptomatic (e.g., dry or thick saliva) without significant dietary alteration; unstimulated saliva flow >0.2 ml/min	Moderate symptoms; oral intake alterations (e.g., copious water, other lubricants, diet limited to purees and/or soft, moist foods); unstimulated saliva 0.1 to 0.2 ml/min	Inability to adequately aliment orally; tube feeding or TPN indicated; unstimulated saliva	-	-

Dysgeusia will be assessed using the NCI CTCAE version 4.0 [25] as follows:

Adverse Event	Grade				
	1	2	3	4	5
Dysgeusia	Altered taste but no change in diet	Altered taste with change in diet (e.g., oral supplements); noxious or unpleasant taste; loss of taste	-	-	-

Dermatitis will be assessed using the NCI CTCAE version 4.0 [25] as follows:

Adverse Event	Grade				
	1	2	3	4	5
Dermatitis radiation	Faint erythema or dry desquamation	Moderate to brisk erythema; patchy moist desquamation, mostly confined to	Moist desquamation in areas other than skin folds and	Life-threatening consequences; skin necrosis or ulceration of full	Death

		skin folds and creases; moderate edema	creases; bleeding induced by minor trauma or abrasion	thickness dermis; spontaneous bleeding from involved site; skin graft indicated	
--	--	----------------------------------------	-------------------------------------------------------	---------------------------------------------------------------------------------	--

Trismus

The interincisal distance will be measured in millimeters at the patient's maximum comfortable extent of mouth opening. Measurements will be taken at baseline, the last day of treatment, two-week follow-up, and 3 month follow-up appointments.

Quality of Life

QOL will be assessed at the time of enrollment prior to initiation of treatment, on the last day of treatment, and on the last day of study participation, 3 months after completion of radiation. This will be assessed using the Functional Assessment of Cancer Therapy: General (FACT-G) version 4 (Appendix 11.7).

QOL as related to head and neck cancer will be assessed at each follow-up appointment using the FACT – H&N version 4 (Appendix 11.8).

6.0 Statistical Considerations

6.1 Primary Endpoints:

- The incidence of severe (WHO grade 3-4) oral mucositis in patients treated to a cumulative radiation dose of at least 5000 cGy.
- The incidence of severe (CTCAE v. 4.0 grade 3-5) oral mucositis in patients treated to a cumulative radiation dose of at least 5000 cGy.

6.2 Secondary Endpoints:

- Time to onset of severe (CTCAE v. 4.0 grade 3-4) oral mucositis following the initiation of radiotherapy.
- Mean cumulative radiation dose at time of onset of severe (CTCAE v. 4.0 grade 3-4) oral mucositis.
- Duration of oral mucositis.
- The incidence of pain.
- The incidence of dysphagia (CTCAE v. 4.0 and via diet assessment).
- The incidence of xerostomia (CTCAE v. 4.0).
- The incidence of dysgeusia (CTCAE v. 4.0).
- The incidence of trismus (Measurement of interincisal distance).
- The incidence of radiodermatitis (CTCAE v. 4.0).
- Evaluation of OM-related QOL (via FACT-H&N score).
- Incidence of any grade oral mucositis in patients treated to a cumulative radiation dose of at least 5000 cGy.

6.3 Exploratory Endpoints:

- Proportion of patients with severe (CTCAE v. 4.0 grade 3-4) oral mucositis by 5000 and 7000 cGy.
- Proportion of patients with severe (CTCAE v. 4.0 grade 3-4) oral mucositis by schedule of chemotherapy given (weekly versus Q 3 weeks).
- Time to reach planned dose of radiation therapy.
- Amount of narcotic analgesia use during treatment.
- Assessments of breaks in treatment defined as one of the following:
 - Missing at least 1 chemotherapy treatment;
 - Dose reduction in planned cisplatin administration; OR
 - 3 consecutive days of no RT secondary to mucositis. ~
- Proportion of patients who require feeding tube placement during treatment (excluding patients who received a prophylactic feeding tube prior to the initiation of therapy).
- Percent change in body weight during the course of treatment.

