3.0 SelectionandWithdrawalofSubjects

3.1 StudyDesign

This is a phase II prospective, single-arm, open label trial testing the efficacy of LLLT in prevention of oral mucositis for HNC patients treated with chemoradiotherapy. Primary endpoints are the incidence of severe (assessed separately as CTCAE v. 4.0 grade 3-5 or WHO grade 3-4) OM in patients receiving a cumulative radiation dose of at least 5000 cGy. Secondary endpoints include the time onset to severe OM, mean cumulative radiation dose at the time of OM, duration of OM, the incidence of pain, dysphagia, xerostomia, dysgeusia, trismus, radiodermatitis, and QOL.

All toxicities will be graded by NCI CTCAE v. 4.0. In addition, oral mucositis will also be graded by WHO mucositis grading scale. Dysphagia will also be graded by a dietary assessment. Trismus will be assessed by measurements of the interincisal distance. QOL will be measured by the FACT-H&N assessment.

Previous studies (detailed in Section 2.2, Table 1) indicate that approximately 40% of patients will experience severe OM with radiation and concurrent chemotherapy. The hypothesis in this trial is that the addition of LLLT to this treatment regimen will decrease the rate of severe acute OM to 20%. We plan to enroll 25 patients at our institution in 12 months after the trial opens. The same protocol will be opened separately at the University of Pittsburgh Medical Center (UPMC), where an additional 25 patients will be enrolled. A Data Use Agreement will allow combination of the data for a total of 50 patients to be analyzed.

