3.2 PatientSelection

InclusionCriteria:

1. Willing and able to understand and sign informed consent form approved by the IRB.
2. Males or females greater than or equal to 18 years old.
3. Biopsy-proven HNC including cancers of the nasopharynx, oropharynx, larynx, hypopharynx, or HNC of unknown primary origin amenable to therapy with radiation and concurrent chemotherapy.
4. Patients who are planned to receive definitive or adjuvant radiotherapy with concurrent platinum-based chemotherapy.
5. Patients whose clinical treatment plans include a continuous course of external beam radiotherapy by intensity-modulated radiation therapy (IMRT) and/or image-guided radiation therapy (IGRT), given as a cumulative dose of 5000 – 7000 cGy in single daily fractions of 180 - 200 cGy, combined with a concurrent course of weekly or tri-weekly cisplatin or carboplatin chemotherapy.
6. Karnofsky performance status score >60.
7. Female patients of child-bearing potential must have a negative pregnancy test prior to enrollment.

ExclusionCriteria:

1. Patient has evidence of current mucositis, mucosal ulceration, or unhealed surgical wounds from surgical resection or biopsy.
2. Prior radiation to the head and neck.
3. Patients with gross tumor involvement of the oral cavity or oral mucosa.
4. Patient planned to receive altered fractionation radiotherapy or multiple fractions per day
5. Patient is using a pre-existing feeding tube for nutritional support at the time of study entry.
6. Women who are pregnant or breast-feeding.
7. Patient plans to receive concurrent chemotherapy, other than the regimens specified in the inclusion criteria.
8. Patients who have chronic immunosuppression or are on current immunosuppressive therapies.
9. Patients who have a contraindication to radiation therapy.
10. Patients enrolled on another investigational trial for oral mucositis prevention.
11. Life expectancy of less than 3 months.
12. Unable or unwilling to adhere to study-specified procedures.

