3.3 Withdrawal of Subjects

Any subject, having previously provided informed consent to participate in the protocol, is free to withdraw from the study at any time for any reason without prejudice to their future medical care by the physician or at the study site. The Investigator or Sponsor may also withdraw the subject at any time in the interest of subject safety. The primary reason for withdrawal must be recorded.

Subject participation may be terminated prior to completion of the clinical study for any of the following reasons:

1. Unacceptable toxicity
2. Death
3. Lack of efficacy
4. Withdrawal by subject
5. Lost to follow-up
6. Non-compliance with study treatment (Subjects who miss >20% of planned LLLT treatments will be considered non-compliant with the protocol)
7. Study physician decision in the best interest of subject safety
8. Pregnancy
9. Major protocol deviation that can affect the safety or efficacy of study population
10. Study terminated
11. Other

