6.4 Sample Size

Previous studies (detailed in Section 2.2, Table 1) indicate that approximately 40% of patients will experience severe OM with radiation and concurrent chemotherapy. The hypothesis in this trial is that the addition of LLLT to this treatment regimen will decrease the rate of severe acute OM to 20%. A sample size of 45 yields 90% power to detect a difference of 0.20 using an exact one-sided binomial test with a Type I error of 0.05. A total of 50 patients are required to ensure that there are at least 45 compliant with the treatment schedule. Subjects who miss >20% of planned LLLT treatments will be considered non-compliant with the protocol. All patients should be enrolled in 12 months after the trial opens. We plan to enroll 25 patients at our institution. The same protocol will be opened separately at the University of Pittsburgh Medical Center (UPMC), where an additional 25 patients will be enrolled. A Data Use Agreement will allow combination of the data for a total of 50 patients to be analyzed.

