6.5 Analysis

Primary endpoint

If 12 or fewer out of the 45 evaluable severe OM events occur (WHO grade 3-4 or CTCAE v. 4.0 grade 3-5 oral mucositis), we will reject the null hypothesis that the occurrence of severe OM is 0.4 with the addition of LLLT therapy. Point and 90% confidence intervals (using Wilson's method) will also be estimated to describe the primary endpoint.

Secondary endpoints

Descriptive statistics (point and exact 90% confidence interval estimates from the resultant Kaplan-Meier curve) will be generated for the time-to-severe OM and duration of severe OM endpoints. Point and 90% confidence intervals (using Wilson's method) will also be estimated to describe the binary endpoints. Continuous endpoints will be described by 90% confidence intervals using the t-distribution.

Exploratory endpoints

Similar descriptive analyses as described in the above paragraph will be used for the binary, time-to-event and continuous endpoints.

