6.6 Evaluation of Toxicity

All registered patients will be evaluated for toxicity probably related to the treatment. There have been no reported toxicities directly attributed to intraoral or extraoral LLLT. No systemic toxicities (e.g fever, nausea, fatigue) are anticipated or have been reported in association with oral LLLT. No specific toxicity is expected attributable to LLLT due to the addition of LLLT in patients receiving radiation with concurrent chemotherapy. Toxicity data will be collected at least weekly during the course of treatment to ensure the validity of this claim.

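### Both primary endpoints leave out patients who stop below 5000 cGy, so an observed severe case can drop out of the primary test, which favours rejecting 0.40

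*Combined protocol and SAP*

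**What the plan says.** Section 6.1 gives two primary endpoints, one on the WHO scale and one on CTCAE. Both carry the same condition; the WHO version reads "The incidence of severe (WHO grade 3-4) oral mucositis in patients treated to a cumulative radiation dose of at least 5000 cGy". Section 3.1 repeats it as severe "OM in patients receiving a cumulative radiation dose of at least 5000 cGy". Eligibility in 3.2 already requires radiotherapy "given as a cumulative dose of 5000 – 7000 cGy in single daily fractions of 180 - 200 cGy".

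The number tested is described in three ways. Section 6.4 says "A total of 50 patients are required to ensure that there are at least 45 compliant with the treatment schedule", and under 3.3 and 6.4 "Subjects who miss >20% of planned LLLT treatments will be considered non-compliant with the protocol". Section 6.4 then adds "A Data Use Agreement will allow combination of the data for a total of 50 patients to be analyzed". The decision rule in 6.5 begins "If 12 or fewer out of the 45 evaluable severe OM events occur". The term *evaluable* is not defined, and no cutoff is given for any n other than 45.

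On safety, 6.6 states "All registered patients will be evaluated for toxicity probably related to the treatment", but 6.7 says that OM arising under LLLT will not count as a treatment-related toxicity. The toxicity evaluation therefore does not bring a lost OM case back.

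**The concern.** Dose received is known only after treatment starts. Because every eligible patient is planned for at least 5000 cGy, the condition selects on what happens during treatment. A patient with recorded severe OM who stops at, say, 4600 cGy is in neither numerator nor denominator of the primary test. Removing an event lowers the observed rate and favours declaring LLLT effective. Removing a patient without severe OM does the opposite. With a single arm, no concurrent group is exposed to the same selection.

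The protocol gives some reason to think that loss could depend on outcome. Section 2.1 links mucositis to unplanned interruptions, 6.3 counts radiotherapy breaks caused by mucositis, and 4.3 holds LLLT during a radiotherapy break. None of these says that patients stop below 5000 cGy. The margin also varies with the plan. At 5000 cGy, one 200 cGy fraction never made up leaves 4800 cGy and excludes the patient. At 7000 cGy, more than 2000 cGy must be lost.

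**Working it through.** **Inputs from the documents.** Null rate 0.40, target rate 0.20, exact one-sided binomial test, type I error 0.05, n = 45, 50 enrolled (6.4); reject at 12 or fewer (6.5). **Assumed.** Exclusion rates, because the documents give none.

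**1. The plan's own figure.** P(X ≤ 12 | 45, 0.40) = 0.0446 and P(X ≤ 12 | 45, 0.20) = 0.9005. A cutoff of 13 would give 0.0836. The stated sample size, power and cutoff are correct.

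**2. Cutoff at other n.** Let k(n) be the largest k with P(X ≤ k | n, 0.40) ≤ 0.05.

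| n | k(n) | Alpha | Power at 0.20 | Alpha if 12 is used |
|---|---|---|---|---|
| 42 | 11 | 0.0449 | 0.882 | 0.0860 |
| 43 | 11 | 0.0354 | 0.865 | 0.0695 |
| 44 | 11 | 0.0277 | 0.846 | 0.0559 |
| 45 | 12 | 0.0446 | 0.901 | 0.0446 |
| 46 | 12 | 0.0354 | 0.886 | 0.0354 |
| 47 | 12 | 0.0279 | 0.869 | 0.0279 |
| 48 | 13 | 0.0442 | 0.916 | 0.0219 |
| 49 | 13 | 0.0353 | 0.903 | 0.0171 |
| 50 | 13 | 0.0280 | 0.889 | 0.0133 |

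At n = 50 the 12 rule has power 0.814.

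**3. Single cases.** 14/50 gives p = 0.054 and does not reject. If one of the 14 stops short, 13/49 gives p = 0.035 and rejects. In the other direction, 13/50 gives p = 0.028; losing three patients without severe OM gives 13/47, p = 0.055.

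**4. Type I error under the dose condition.** Let a severe case be excluded with probability s and any other patient with probability t. Overall exclusion is 0.40s + 0.60t. The rate among those left is r = 0.40(1 − s) / [0.40(1 − s) + 0.60(1 − t)]. The number left, n, is binomial from 50. Type I error is the sum over n of P(n) × P(X ≤ k(n) | n, r).

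| Excluded overall | Unrelated to OM (s = t) | Severe only | Non-severe only |
|---|---|---|---|
| 2% | 0.034 | 0.049 (s = 5%) | 0.026 (t = 3.3%) |
| 5% | 0.036 | 0.087 (s = 12.5%) | 0.018 (t = 8.3%) |
| 10% | 0.036 | 0.187 (s = 25%) | 0.008 (t = 16.7%) |

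Milder dependence gives intermediate values: 0.049 at 5% (s = 7.5%, t = 3.3%) and 0.067 at 10% (s = 15%, t = 6.7%). The 10% row matches the 50-to-45 allowance in 6.4, although that allowance is for LLLT compliance, not dose.

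**5. Two candidate repairs.** Suppose 10% leave before OM can develop.
- Kept as non-events: the rate becomes 0.90 × 0.40 = 0.36, and P(X ≤ 13 | 50, 0.36) = 0.090.
- Left out, with every recorded severe case kept: type I error 0.036, power 0.877.

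Suppose instead that 10% of patients without severe OM leave and are left out (s = 0, t = 10%). The rate rises from 0.40 to 0.40 / (0.40 + 0.60 × 0.90) = 0.426. Type I error is 0.016 and power 0.815.

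**The case against.** **The direct support for outcome-related loss is thin.** Section 2.1 speaks of interruptions, not of ending below 5000 cGy, and a missed fraction may be made up. The two randomised chemoradiation trials in Table 1 that state a total dose used 66 and 70.2 Gy; at such doses a patient would have to lose more than 1600 or 2020 cGy. This stands. A reader might infer that the plan's type I error is inflated, but the documents do not show that: at 2% excluded it stays below 0.05 even if every loss is a severe case.

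**Early severe cases are not all lost.** A reader might infer that severe OM arising before 5000 cGy is ignored. On a plain reading it counts if the patient goes on to reach that dose. For those who do not, the time-to-onset endpoint in 6.2 has no dose limit and would still report severe OM by CTCAE. The information is missing from the primary test, not from the trial.

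**The limit might mean planned dose.** That would make it redundant with 3.2, and the wording in 3.1 and 6.1 points to dose delivered.

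**The cutoff can be derived.** Section 6.4 fixes the test, the null rate and alpha, so k(n) follows. The 0.056 to 0.086 figures arise only if 12 is carried over to n = 42 to 44. The likely reading of *evaluable* is LLLT-compliant. Both points are therefore secondary, but neither is written down.

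**Analysing everyone who starts LLLT looks simpler.** If early leavers without severe OM count as non-events, that too favours rejection: 0.090 in step 5, against 0.036 under the plan's exclusion in the same scenario. This objection stands and shapes the fix.

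**Conclusion.** The point holds in a limited form and should be fixed. By its own wording, the primary test drops a patient with recorded severe OM who stops below 5000 cGy, and each such loss favours rejecting 0.40. How much this matters rests on assumed exclusion rates: nothing beyond 0.05 at 2%, up to 0.087 at 5% and up to 0.187 at 10%. The last figure requires a quarter of severe cases and no other patients to be lost. Loss confined to patients without severe OM makes the test conservative. The sample size and the 12/45 rule are sound at n = 45. The undefined analysis set and the single cutoff are gaps in wording that could be closed after outcomes are known; nothing in the documents suggests that this is intended.

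**What to change.** - In 3.1, 6.1 and 6.5, define the evaluable set as all patients who start LLLT and either have severe OM recorded, at any cumulative dose and any level of LLLT compliance, or reach 5000 cGy. Every observed severe OM is then an event, including one recorded before withdrawal. Only early leavers without severe OM are left out.
- Apply the same principle to the any-grade OM endpoint in 6.2, which carries the same dose limit.
- Reconcile 45 with 50 in 6.4 and 6.5. State that the cutoff is the largest k with P(X ≤ k | n, 0.40) ≤ 0.05 at the realised n: 11 for n = 42 to 44, 12 for 45 to 47, 13 for 48 to 50.
- Report three sensitivity analyses: all who start LLLT with early leavers counted as non-events; the same set with them counted as events; and the compliant set that reached 5000 cGy.

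**Cost.** Wording only. OM is already graded weekly, so no patients or visits are added. Power at a 20% rate is 0.889 if all 50 are evaluable, against 0.9005 at 12/45. It is 0.877 or 0.815 in the two scenarios of step 5. The estimated rate leans upward when patients without severe OM leave. If leavers were on their way to severe OM, leaving them out would understate the rate; counting them as events shows how far. That is too severe for the primary test: if 5% of patients without severe OM leave, the event rate becomes 0.20 + 0.05 × 0.80 = 0.24, and power at 13/50 falls to 0.698.
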